1. To compare the efficacy in reducing the frequency of migraine attacks under prophylactic treatment with Memantine at a rate of 20 mg divided into two doses per day against sodium Valproate at a rate of 1000 mg divided into two doses per day for three months in adult patients with migraine.

B. Specific objectives

1. To evaluate the baseline frequency of migraine attacks in adult patients with migraine 28 days prior to the study.
2. To evaluate the frequency of migraine attacks of the group - treatment with sodium Valproate for three months, in adult patients with migraine.
3. To evaluate the frequency of migraine attacks of the group - treatment with Memantine for three months, in adult patients with migraine.

C. Secondary objectives

1. Evaluate the response rate to treatment.
2. Assess migraine disability using MIDAS (Migraine Disability Assessment) before and after treatment.
3. To assess pain intensity in migraine attacks with the visual analog scale (VAS) before and after treatment.
4. Identify adverse effects to sodium Valproate and Memantine.

SUBJECTS AND METHODS

Site

The study was conducted at the outpatient clinic of the Hospital Central [name] Prieto, San Luis Potosí.

Design

Prospective, randomized, double-blind, controlled clinical trial.

Inclusion criteria

1. Men and women from 18 to 65 years old.
2. Diagnosis of episodic migraine according to the ICHD-III of the IHS at least one year prior to the study.
3. Must present at ≥ 4 - ≤ 8 migraine attacks per month.
4. Not receiving prophylactic treatment for migraine headache.
5. Sign informed consent

Exclusion Criteria

1. Pregnant or breastfeeding patients.
2. Patients with other types of non-migraine headache.
3. Allergy to Sodium Valproate and/or Memantine
4. Being a carrier of systemic disease (infectious, immunological or metabolic processes) or cardiovascular disease (myocardial, coronary or valvular heart disease) that prevents participation in the study.

Elimination Criteria

1. Patients who do not tolerate the study drug during titration.
2. Patients who voluntarily leave the study.
3. Patients lost to follow-up.

Variables

Dependent's

1. Frequency of migraine attacks: Defined as the number of migraine attacks presented during the month. It is a continuous variable.
2. Treatment response rate: Defined as a decrease equal to or greater than 50% in the frequency of days with migraine compared to the baseline situation. It is a continuous variable.

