Recruitment was carried out from July 2019 to August 2020 in the outpatient service of Neurology, Referral and Emergency of the Central Hospital. Patients who met the inclusion criteria and signed the informed consent form participated in the study. At the time of recruitment, they will be randomized by computer by an external collaborator of wide experience, assigning them a number and an external collaborator will distribute them in one of the two groups. Double-blinding will be performed, both for the researcher and for the participant, the only one who knew which group they were assigned to was the one who performed the randomization.

A total of 4 visits were made, with a time interval of one month for each visit.

Visit 1 (Week 0): a clinical history was taken, a physical examination was performed, the informed consent form was signed (Annex 1), and the inclusion and exclusion criteria form (Annex 2) was filled out by the researcher. A "Migraine diary" (Annex 3) was provided to the patient where the migraine attacks were recorded to identify the baseline characteristics such as frequency, intensity, duration.

Visit 2 (Week 4): the patient was given the medication assigned by the corresponding randomization. Memantine or VPA was prescribed as an oral tablet at night for one week and then increased in the second week to one tablet in the morning and at night. The baseline MIDAS survey was performed to identify migraine disability. The baseline "Migraine Diary" was collected and a new "Migraine Diary" was provided.

Visit 3 (Week 8): Frequency of migraine attacks, adverse effects and tolerability of treatment were assessed by the investigator. The "Migraine Diary" was collected and a new "Migraine Diary" was provided. The corresponding medication was given for four weeks.

Visit 4 (Week 12): Visit 3 (Week 8): Migraine attack frequency, adverse effects and tolerability of treatment were assessed by the investigator. The "Migraine Diary" was collected and a new "Migraine Diary" was provided. The corresponding medication was given for four weeks.

Visit 5 (Week 16): Frequency of migraine attacks, adverse effects and tolerability of treatment were evaluated by the investigator. The "Migraine Diary" was collected. The MIDAS survey was performed again to assess post-treatment disability.

Financing

A donation of the pharmacological treatment Memantine and sodium Valproate was received from the Torrent Pharma Laboratory (Annex 5).

STATISTICAL ANALYSIS

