Sample size calculation

Normal distribution model: $x=Z(c/100)^2 r(100-r)$. $n=Nx/((N-1)E^2+x)$ $E=\text{Sqrt}[(N-n)x/n(N-1)]$. With a margin of error of 5%, a confidence level of 95%, with a prevalence of migraine in the general population of the State of San Luis Potosi of 271800 with a distribution response of 15%.¹⁹ The recommended sample size is 196 participants. Due to the fact that a pilot study will be conducted, 10% of the sample size will be taken to make it representative, a sample size of 20 participants for each group is decided.²⁰

Descriptive statistical analysis of the variables of interest will be performed. For continuous variables, analysis will be performed using the Student's t-test. The number of participants (n) and the final analysis was calculated using R (56). Alpha, the probability of type 1 error was set to 0.05 and the power was set to 0.8 which resulted in the probability of a type 2 error of 0.2, given that we limited to 20 participants per treatment, delta was estimated with this restriction.

ETHICS

Risk category: Risk greater than minimal.

Authorization will be requested from the Research Ethics Committee of the Hospital Central "[name] Prieto". The study will be performed according to the Mexican Official Standard for the conduct of clinical studies in humans NOM-012-SSA3-2012²¹, and international standards (Declaration of Helsinki²² and International Harmonized Guide (ICH) of Good Clinical Practices²³) The diagnostic maneuvers that will be used are considered of higher than minimal risk because it is an interventional study according to article 17 of the regulations of the General Law of Health²³ on Health Research.

In addition, it is a priority to safeguard the physical and mental integrity of the patient, and privacy is respected by maintaining the confidentiality of the data at all times during the research, as well as the data obtained at the end of it. The consent of the legal subjects will be obtained through a document specifying the objective of the study, the duration, as well as the methods and medications that they will receive randomly.

RESULTS

Eighty-seven patients were evaluated, of which only 33 patients were included in the study. In the Memantine group with 16 patients and 17 in the Sodium Valproate (VPA) group; only 27 patients concluded the study.

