Being a carrier of systemic disease (infectious, immunological, or metabolic processes) or cardiovascular (myocardial, coronary, or valvular disease) prevents their participation in the study.

Primary outcomes

The primary outcome was the difference in change from baseline in the monthly attack frequency at week 12 between the two groups (using migraine diary).

Secondary outcomes

1. Evaluate the response rate to treatment.
2. Evaluate migraine disability using MIDAS (Migraine Disability Assessment) before and after treatment.
3. Identify adverse effects to sodium valproate and memantine.

Statistical analysis.

Statistical analysis

Descriptive statistical analysis of the variables of interest will be carried out.

For continuous variables, their research will be analyzed using the t-student test.

First, the number of participants (n) and the final analysis were calculated using R (56).

Alpha, the probability of a type 1 error was set to 0.05.

The power was set to 0.8, resulting in a type 2 error of 0.2.

Since we were limited to 20 participants per treatment, the delta was estimated with this restriction.

Since we were limited to 20 participants per treatment, the delta was estimated with this restriction.

Results

Table 1. Baseline Demographic and Clinical Characteristics

[figure not shown]
Characteristic	Memantine	Sodium Valproate	p
Female sex – no (%)	13(81.25%)	13 (76.47%)	
Male sex – no (%)	3 (18.75%)	4 (23.52%)	0.54*
Age	$31.18 \pm 10.94^{\$}$	$31.58 \pm 7.51^{\$}$	0.91*
A family history of migraine (%)	10 (62.5%)	9 (52.94%)	0.82*
Clinical characteristics			
Photophobia - no (%)	14 (87.50%)	16 (94.12%)	0.48*
Phonophobia - no (%)	16 (100%)	10 (58.82%)	0.60*
Nausea - no (%)	14 (87.5%)	17 (100%)	0.23*
Disability activities of daily living	15 (93.75%)	16 (94.12%)	0.74*
Migraine without aura	13 (81.25%)	13 (76.47%)	0.54*
Migraine with aura	3 (18.75%)	4 (23.52%)	

* Fisher's exact test

§ Plus-minus values are means \pm SD

PRIMARY OUTCOME

[figure not shown]
Monthly attack migraine frequency before and after treatment

Secondary outcome

Evaluate the response rate to the treatment

Figure 2. Days with migraine before and after treatment

Adverse Events

Table 2. Adverse Events According to Group

	Memantine (n=17)	Sodium Valproate (n=16)	Clinical severity CTCAE*
Any adverse event	8	7	
Somnolence	4	6	Grade 1-Mild
poor concentration	2	0	Grade 1-Mild
Parasomnia	0	1	Grade 1-Mild
Dizziness	2	0	Grade 1-Mild

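### The elimination criteria act as an unstated completers-only rule with no sensitivity analysis, and the printed means do not come from one patient set (memantine decrease 4.21 in Results, 4.39 in Discussion)

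*Protocol*

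**What the plan says.** The Protocol (Subjects and methods, Elimination Criteria) lists three grounds: "Patients who do not tolerate the study drug during titration", voluntary withdrawal, and "Patients lost to follow-up". It does not say whether an eliminated patient stays in the analysis.

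On timing, the Work Plan says "At the time of recruitment, they will be randomized by computer by an external collaborator of wide experience". Drug is handed over one month later, at Visit 2 (week 4), when "the patient was given the medication assigned by the corresponding randomization".

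The SAP (Primary outcomes) is explicitly comparative: "The primary outcome was the difference in change from baseline in the monthly attack frequency at week 12 between the two groups". Its analysis section offers "For continuous variables, their research will be analyzed using the t-student test", with descriptive statistics, alpha 0.05 and power 0.8. The Protocol's Statistical Analysis section has the same content. Neither names an analysis set, a way of handling missing outcomes, or a sensitivity analysis.

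On numbers, Protocol Results state "In the Memantine group with 16 patients and 17 in the Sodium Valproate (VPA) group; only 27 patients concluded the study". The Summary splits the completers as 14 memantine and 13 valproate. The Discussion attributes three losses to follow-up and three to COVID-19. SAP Table 2 heads its first column "Memantine (n=17") and gives valproate 16.

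**The concern.** All three elimination grounds arise after randomisation, and some may precede the first dose. Applied as written, the list turns a randomised comparison into one between those who finished in each arm. With 6 of 33 (18%) missing from a two-arm comparison of this size, the treatment of those six should be stated, and its influence shown.

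The reporting has a related problem. If baseline means are taken over everyone randomised and changes over completers, a reader who subtracts one printed mean from another gets a figure that describes no group of patients. The Discussion appears to do this.

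At stake are the primary between-group estimate, the response claim, and the conclusion of no inferiority, which does not say that it rests on completers. The lack of a non-inferiority margin is a different defect and is not argued here.

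**Working it through.** **1. Attrition.** Randomised 16 and 17 (Protocol Results); completed 14 and 13 (Summary). Losses: 2/16 = 12.5% and 4/17 = 23.5%; total 6/33 = 18.2%. Fisher's exact p = 0.66, so no clear difference between arms.

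**2. Completer comparison.** Inputs from Protocol Results: decrease 4.21 (SD 1.76, n 14) and 4.5 (SD 1.39, n 13). The readable text gives only within-arm p-values for attacks, so this is a reconstruction.
- Difference, memantine minus valproate: 4.21 - 4.5 = -0.29.
- SE = sqrt(1.76²/14 + 1.39²/13) = sqrt(0.2213 + 0.1486) = 0.608; Welch df 24.4, t = 2.062.
- 95% CI: -0.29 ± 1.254 = -1.54 to 0.96.

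**3. Sensitivity to the six losses.** Let the missing patients average a fraction f of their own arm's completer change. The arm means become 4.21(14 + 2f)/16 and 4.5(13 + 4f)/17.

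| f | Memantine | Valproate | Difference | 95% CI |
|---|---|---|---|---|
| 1 | 4.21 | 4.50 | -0.29 | -1.58 to 1.00 |
| 0.5 | 3.95 | 3.97 | -0.02 | -1.45 to 1.41 |
| 0 | 3.68 | 3.44 | +0.24 | -1.53 to 2.02 |

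The intervals use multiple imputation from the summary statistics with the completers' spread. The difference is zero where 71.57(14 + 2f) = 72(13 + 4f), that is f = 65.98/144.86 = 0.455.

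**4. Response.** As printed, 27 of 27. With dropouts counted as non-responders: 14/16 = 87.5% v 13/17 = 76.5%, difference 11.0 points (Newcombe 95% CI -16.3 to 36.4). That difference comes from attrition alone.

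**5. Do the means subtract?** On one patient set, baseline mean minus post-treatment mean must equal the mean decrease.

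| Row (Protocol Results) | Baseline - post | Printed decrease | Smallest gap, all rounded | Smallest gap, all truncated |
|---|---|---|---|---|
| Memantine attacks | 5.31 - 0.93 = 4.38 | 4.21 | 0.155 | 0.15 |
| Valproate attacks | 5.35 - 0.77 = 4.58 | 4.5 | – | none |
| Memantine days | 4.3 - 0.23 = 4.07 | 3.9 | 0.065 | 0.06 |
| Valproate days | 5.5 - 0.27 = 5.23 | 4.88 | 0.29 | 0.33 |

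Example, memantine attacks rounded: (5.305 - 0.935) - 4.215 = 0.155. Valproate attacks could be truncation, so no mismatch is claimed. The Discussion's 4.39 is 5.31 - 0.92, and exceeds the Results figure by 4.39 - 4.21 = 0.18.

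**6. Which patients?** If attacks are whole monthly counts, the memantine baseline fits 85/16 = 5.3125 and no total over 14. Post-treatment fits 13/14 = 0.929, and the decrease fits 59/14 = 4.214. That is an all-randomised baseline beside a completer change. The implied completer baseline is (59 + 13)/14 = 5.14.

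**7. MIDAS.** The Annex 4 items that are legible count days, so whole scores are assumed.
- Memantine baseline 60.87: over 14 patients the nearest totals give 852/14 = 60.857 and 853/14 = 60.929, and neither prints as 60.87. Totals over 15 (913/15 = 60.867) or 16 (974/16 = 60.875, truncated) can.
- Valproate baseline 51.92: over 17, 882/17 = 51.882 and 883/17 = 51.941 do not fit.

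So the memantine baseline is not on the 14 completers and the valproate baseline is not on all 17 randomised.

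**8. SAP Table 2.** Any adverse event on its headings: 8/17 = 47.1% v 7/16 = 43.8%. On the sizes in Results and Table 1: 8/16 = 50.0% v 7/17 = 41.2%.

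**The case against.** The best defence is that a rule does exist. A list headed as elimination criteria, followed by a Discussion saying that only 27 patients were included, is naturally read as a completers-only analysis. The trial calls itself a pilot and discloses its attrition. Three of the six losses are put down to COVID-19 and none to intolerance. Much of this stands: it would be wrong to say that the handling of losses has no basis in the documents. What remains is that the rule is implicit, excludes patients for post-randomisation events, and has no sensitivity analysis beside it. The stated limitation concerns sample size, not the analysis set.

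A reader might infer from the working that the sign of the primary estimate hangs on the missing patients. That goes too far. The sign turns only if they average below about 45% of the completers' change, +0.24 needs the extreme of zero change in all six, and every interval includes zero.

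A reader might also infer patient numbers from the migraine-day means, since 0.23 and 0.27 fit 3/13 and 3/11. The adjacent valproate decrease of 4.88 fits 78/16 or 83/17 but no total over 11 or 13. Either days are not whole numbers or the row contains an error, so no counts are inferred. Likewise the valproate MIDAS baseline fits 13 (675/13), but also 12 (623/12) and, truncated, 14 (727/14). Only the exclusion of 17 is safe.

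Finally, Protocol Results mention the three months before treatment. If baselines were three-month averages, the whole-count attribution in step 6 weakens, but the subtraction mismatch does not. Some figures are not shown and may give n or patient disposition.

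**Conclusion.** The point holds and should be fixed. The effective analysis rule is completers-only, left implicit, with no all-randomised analysis or sensitivity analysis planned. The change results are presented on 27 of 33 patients.

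The completer difference is -0.29 attacks (95% CI -1.54 to 0.96). Plausible to extreme handling of the six moves it by about 0.5 attacks without any interval excluding zero. The documents do not support a claim that the result is biased in either direction: the reasons for loss are not split by arm in the readable text, and dropout does not clearly differ between arms.

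That 4.39 contradicts 4.21, and that the memantine attack row and both migraine-day rows do not subtract, needs no assumption beyond consistent rounding or truncation. For migraine days the cause may be different patient sets or an arithmetic error. Naming the sets for attacks and MIDAS assumes whole counts and is less certain. The reversed arm sizes in SAP Table 2 are a separate reporting error.

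**What to change.** - State that the elimination criteria record leaving treatment or follow-up and do not remove a patient from the analysis.
- Add to the SAP, labelled post hoc because it already contains results, an analysis of all randomised patients in their assigned arm using the available diaries. Put beside it the completer analysis and simple missing-data sensitivity analyses, including zero change for attacks and dropouts as non-responders for response.
- Give the six losses by arm and reason, and before or after first dose, unless a figure not shown already does so.
- Replace 4.39 with the same-patient change (4.21 if the data confirm it). Report baseline, post-treatment and change on the same patients, with n, for attacks, migraine days and MIDAS.
- Recheck the migraine-day rows and the response denominator against the data before repeating 27 of 27.
- Correct the SAP Table 2 arm sizes.
- Label the response and no-inferiority statements as completer results.

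This needs wording changes and re-analysis of existing diaries, with no new data. The cost is wider intervals and less favourable sensitivity figures. Modelling will add little if the six returned no on-treatment diary, which the documents do not say; the reporting corrections are worth making regardless.

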Migraine with aura	3 (18.75%)	4 (23.52%)

Secondary objectives. - Treatment response rate which is referred to as the decrease of equal or more than 50% of migraine days. In the Memantine group with pretreatment migraine days 4.3 (SD+ 1.93) and post treatment 0.23 (SD+ 0.44) with a mean decrease in migraine days of 3.9 (SD+ 1.89) $p <<0.001$. In the Sodium Valproate group with pretreatment migraine days 5.5 (SD+ 1.25) and post treatment 0.27 with mean decrease of migraine days 4.88 with (SD+ 1.29) $p <<0.001$ ([Figure](#))

4). In both groups the 27 patients presented a successful treatment response rate, in the Memantine group with a decrease in percentage of migraine days average 94% (SD+ 9.95) and in the Sodium Valproate group 93.18% (SD+ 14.50).

The intensity of migraine was evaluated with the Visual Analog Scale (VAS) pre and post treatment. In the Memantine group pre-treatment VAS 8.5 (SD+ 1.36) and post-treatment 4.28 (3.65) $p < 0.00014$. In the VPA group with pretreatment VAS 8.94(SD+ 0.87) and post treatment 2.5 (SD+ 0.87) $p < 0.0000012$.

Migraine disability assessed with MIDAS in the Memantine group with MIDAS mean pretreatment 60.87 (SD+ 25.22) and post-treatment 15.57 (SD+ 14.32) $p < 0.000004$. In the Sodium Valproate group with MIDAS pretreatment of 51.92 (SD+ 22.67) and post treatment 10.53 (SD+ 19.97) $p < 0.00002$ ([Figure 5](#)).

Figure 5. MIDAS pre- and post-treatment in both groups.

Side effects: The side effects presented by the patients were not severe in their totality, eight patients in the Memantine group presented non-severe side effects and seven patients in the sodium valproate group ([Table 2](#)), the most frequent in both groups being somnolence.

Table 2 . Side effects

	Memantine	Sodium Valproate
None		
Drowsiness		
Lack of concentration		0
Parasomnia	0	1
Dizziness		0
Total		

DISCUSSION

This is the first randomized double-blind pilot clinical trial comparing the efficacy and safety of memantine with a first-line treatment, sodium valproate.

With the objective of recruiting 40 patients as a pilot study, the Neurology outpatient clinic was suspended due to the COVID-19 pandemic, we finally managed to recruit 33 patients, 3 lost follow-up and 3 dropped out of the study due to COVID-19 and only 27 patients were included.

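### Treatment response is a yes/no outcome labelled continuous, so the plan's only inferential rule assigns it a t-test that cannot be computed on the reported data, and no binary analysis is specified

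*Protocol*

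**What the plan says.** The protocol's variable list (Subjects and methods, Variables, dependent variable 2) begins "Treatment response rate: Defined as a decrease equal to or greater than 50% in the frequency of days with migraine compared to the baseline situation" and then gives the type: "in the frequency of days with migraine compared to the baseline situation. It is a continuous variable". Other entries carry different types: MIDAS is ordinal and gender is nominal.

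The protocol's Statistical analysis section has one inferential rule: "For continuous variables, analysis will be performed using the Student's t-test". The SAP repeats it under Statistical analysis: "For continuous variables, their research will be analyzed using the t-student test". Neither says whether the t-test is paired or two-sample, and neither names a test for a binary outcome. The SAP lists response as its first secondary outcome, "Evaluate the response rate to treatment", with no test, comparison, population or missing-data rule. The only categorical test named is "Fisher's exact test", in a footnote to the SAP baseline table.

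The protocol's Results (Secondary objectives) state that all 27 completers responded. They also give before/after p-values for mean migraine days within each arm, and a mean percentage fall: "in the Memantine group with a decrease in percentage of migraine days average 94% (SD+ 9.95") for memantine and 93.18% (SD 14.50) for valproate. They give no between-arm difference, interval or test for response.

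**The concern.** A threshold outcome takes two values per patient and is summarised as a count over a denominator. Labelling it continuous routes it to a comparison of means, and the plan has no other route. If the label was meant for the percentage fall in migraine days, then the 50% definition has no analysis at all. Either reading needs correction.

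At stake is how much the response result can carry. The protocol concludes that memantine was not inferior to valproate. A response of 100% in both arms looks like strong support until an interval is put around the difference. The plan does not ask for one.

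**Working it through.** **The plan's own figure.** The survey formula with Z = 1.96, r = 15, N = 271800 and E = 5 gives x = 1.96² × 15 × 85 = 4898.04 and n = 271800 × 4898.04 / (271799 × 25 + 4898.04) = 195.78, or 196 as stated. It estimates a prevalence and says nothing about comparing response between arms. The documents give no response effect size or margin.

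**Inputs.** Randomised: 16 memantine, 17 valproate (protocol Results). Completers: 14 and 13 (protocol Summary). Responders: all 27 completers, hence 14/14 and 13/13. Alpha: "Alpha, the probability of type 1 error was set to 0.05", taken as two-sided because the documents do not say. Differences are memantine minus valproate.

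**The test the rules assign.** For 0/1 data the pooled variance is [n1·p1(1−p1) + n2·p2(1−p2)] / (n1 + n2 − 2). With p1 = p2 = 1 it is 0, so t = 0/0 and there is no p-value. Such data need not be unusual: if both true rates were 95% (an assumption), all 27 would respond with probability 0.95^27 = 0.25.

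**Binary analysis, completers.**
- Exact lower limit when all n respond = 0.025^(1/n): 0.025^(1/14) = 76.8% and 0.025^(1/13) = 75.3%; both upper limits are 100%.
- Wilson lower limit when all n respond = n/(n + 1.96²): 14/17.84 = 78.5% and 13/16.84 = 77.2%.
- Newcombe limits for the difference: 0 − (100 − 78.5) = -21.5 and 0 + (100 − 77.2) = +22.8 points.
- Fisher's exact test: p = 1.00.

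**Sensitivity analysis, all randomised.** There are 33 − 27 = 6 non-completers: 2 memantine and 4 valproate. Counting them as non-responders gives 14/16 = 87.5% against 13/17 = 76.5%, difference 11.0 points, Newcombe 95% CI -16.3 to +36.4, Fisher p = 0.66.

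**False-positive rate of the t-test on 0/1 data.** Exact enumeration at 20 per arm, nominal 0.05, common response rates from 50% to 95%: t-test 0.012 to 0.053; Fisher 0.002 to 0.025.

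**Denominators.**
- SAP Table 2 heads its columns 17 for memantine and 16 for valproate, the reverse of the protocol Results. Percentages in the baseline table fit 16 and 17 (13/16 = 81.25%, 13/17 = 76.47%). Under the reversed sizes, the sensitivity analysis becomes 14/17 = 82.4% against 13/16 = 81.3%, about 1 point apart.
- The post-treatment mean migraine days are 0.23 (memantine) and 0.27 (valproate). If days are whole numbers, 14 patients can give 3/14 = 0.21 or 4/14 = 0.29, and 13 can give 3/13 = 0.23 or 4/13 = 0.31. Neither arm's mean fits its completer count. A mean of 0.23 fits 3/13, with SD 0.44 as reported if three patients had one day each; 0.27 fits 3/11.

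**The case against.** The strongest reply is that no sentence says response is t-tested, and no such test was run. That is correct. The assignment comes from joining the variable label to the t-test rule, and the SAP does not repeat the label. A reader might infer that the trial analysed 0/1 response data with a t-test. The documents do not support this: the p-values under the response heading belong to mean migraine days, a legitimate continuous variable.

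A reader might also infer that responder proportions went unreported, or that the label caused the lack of a between-arm comparison. Neither holds. The Results say all 27 completers responded, and the primary outcome too is reported with within-arm p-values only, so that gap is general.

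The stated objective is to evaluate the response rate, not explicitly to compare it. But the protocol Summary sets response rate within a comparison of the two drugs in a randomised trial, so a comparison is a fair expectation.

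It is also tempting to say that the true response rate is 27/33 = 81.8% with an 11-point difference between arms. Both figures come from counting non-completers as non-responders, a separate missing-data choice. Three of the six left because of COVID-19 and the other three were lost to follow-up, so that choice is contestable.

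Finally, the t-test does not materially inflate the false-positive rate here, and correcting the type yields no significant difference. Both points stand and limit the severity.

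**Conclusion.** The point holds as a mis-specified secondary outcome. The label contradicts the definition, the only inferential rule then assigns a test that fails on the reported data, and no binary analysis is stated. Correcting the type alone leaves the estimated difference at 0 (p = 1.00) but adds an interval of -21.5 to +22.8 points. With a response deficit of about 21 points for memantine still compatible with the data, and no response margin stated, these data alone cannot support a claim of no inferiority.

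This assumes that the completer counts of 14 and 13 are right and that all were assessed for response. The sensitivity result additionally assumes non-response in all six non-completers.

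**What to change.** 1. Before any comparison, reconcile the arm sizes in SAP Table 2 with the protocol Results, and confirm how many patients per arm contributed migraine-day data after treatment.
2. In the protocol variable list, relabel response as binary. List percentage reduction in migraine days as a separate continuous variable, for description only.
3. In the SAP, add one line: report response as n/N per arm, with the between-arm difference, its 95% CI (method named) and Fisher's exact test. State the analysis population and how non-completers are handled. Show the completer result, with non-completers as non-responders as a sensitivity analysis.
4. Because results already stand in both documents, describe this comparison as specified after the data were seen, and do not rest a non-inferiority statement on response.

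The cost is about two lines of text and no new data. The response result will read less favourably, because 100% in both arms will carry an interval of more than 20 points either way.
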